NEI VFQ-25	National Eye Institute Visual Functioning Questionnaire 25-item Version
NI	near infrared
OCT	optical coherence tomography
OCT-A	optical coherence tomography angiography
PCR	polymerase chain reaction
PD	pharmacodynamics
PK	pharmacokinetic(s)
PRO	patient-reported outcome
Q4W	every 4 weeks
Q6W	every 6 weeks
qAF	quantitative fundus autofluorescence
RCR	Roche Clinical Repository
RPE	retinal pigment epithelium
SAE	serious adverse event
SAP	Statistical Analysis Plan
SD-OCT	spectral domain optical coherence tomography
SNP	single nucleotide polymorphism
ULN	upper limit of normal
VA	visual acuity
YAG	yttrium aluminum garnet

1. **BACKGROUND**

1.1 **BACKGROUND ON GEOGRAPHIC ATROPHY SECONDARY TO AGE-RELATED MACULAR DEGENERATION**

Age-related macular degeneration (AMD) is the leading cause of irreversible blindness in people aged 50 years or older in the developed world (Friedman et al. 2004). The majority of the visual loss occurs in the advanced stage of AMD, which has two clinical forms: a non-exudative form, geographic atrophy (GA), which is characterized by loss of choriocapillaris, retinal pigment epithelium (RPE), and photoreceptors; and an exudative or wet form, which is characterized by choroidal neovascularization (CNV) (Lindblad et al. 2009; Sunness et al. 1999b). The prevalence of GA increases exponentially with age and approximately quadruples per decade beyond 50 years of age. The estimated prevalence of GA in populations of European ancestry at 70 years of age is 0.70%, rising to 2.91% at 80 years of age and 11.29% at 90 years of age (Rudnicka et al. 2012).

In the early stages of GA, patients typically show minimal changes in central visual acuity (VA). However, while central VA may not yet be affected, patients often still experience significant symptoms from visual dysfunction, such as dense parafoveal scotomas (e.g., leading to difficulties with face recognition), delayed dark adaptation, reduced contrast sensitivity, and a decrease in reading rate (Sunness et al. 1995, 1996, 1999a). In the later stages, as the GA lesion expands into the fovea, a profound decrease in central VA occurs with a decline in activities of daily living (Lindblad and Clemons 2005). Moreover, GA is bilateral in most patients with advanced AMD (Lindblad et al. 2009; Sunness et al. 1999b). As such, GA is a significant cause of both moderate and severe central visual loss.

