2.3 SAMPLE SIZE

2.3.1 Determination of Sample Size

Approximately 936 patients will be enrolled in the study. Patients are randomized in a 2:1:2:1 ratio to receive treatment with lampalizumab Q4W, sham Q4W, lampalizumab Q6W, or sham Q6W. Data from the two sham treatment arms will be pooled in the analysis.

The study was originally sized to achieve adequate power for detecting a meaningful reduction rate in the GA area growth for a given lampalizumab dosing frequency compared with pooled sham within each of the biomarker-positive and biomarker-negative groups and to meet health authority requirements for the size of the safety database. At the time of the study design, sample size and power calculations used assumptions based on results from the Phase II Study CFD4870g. For details of the determination of sample size, see study protocol Section 6.1.

As outlined in Section 6.1, the protocol also specified that the Sponsor may conduct a masked evaluation of the variance of the primary efficacy endpoint and study dropout rate before the end of enrollment, with the intent to potentially increase the study sample size if deemed necessary in order to maintain the desired study power. However, such an evaluation was not conducted and the sample size of the study remained unchanged from that originally planned.

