2.3.2 Estimated Power Based on Information from Study GX29633

The primary efficacy endpoint is the change from baseline in GA area at 1 year (48 weeks) as assessed by FAF. As specified in Section 4.5.1, the primary efficacy objectives will be assessed by analysis of the primary efficacy endpoint in the overall patient population and in the biomarker-positive group for each dosing frequency separately.

[Table 2](#) summarizes the power and minimum detectable difference for the primary endpoint analysis when evaluated for the overall patient population and the biomarker-positive group using progression rates and variability assumptions based on data from Study GX29633, a prospective epidemiological study of the progression of GA secondary to AMD (May 2017 interim analysis). Namely, calculations assumed a progression rate (mean change from baseline in GA area at 48-weeks) of 2.08 mm² for both the biomarker-positive and biomarker-negative patient groups and a SD of 1.53 mm² for the change from baseline in GA area at 48-weeks. With these assumptions, 312 patients per lampalizumab treatment arm and 156 patients per sham arm will provide 88% power to declare a difference between each lampalizumab treatment arm and the pooled sham arm in the overall patient population for a targeted difference of 0.42 mm² (approximately 20% reduction relative to sham control) in the change from baseline in GA area at 48 weeks ([Table 2](#)). Estimated power to detect specified differences in the primary efficacy endpoint within the biomarker-positive

patient population is as shown in Table 2. Calculations were based on two-sided t-tests at the $\alpha=0.0496$ level (after adjustment for the four data reviews conducted by the iDMC prior to analysis of the primary efficacy endpoint), with the assumption of a 15% dropout rate by 48 weeks.

Table 2 Power and Minimum Detectable Difference for Analysis of Primary Endpoint Using Assumptions Based on the Epidemiological Study GX29633

Endpoint Summary and Population	Target Treatment Effect	Two-Sided $\alpha=0.0496$	
		Power	MDD
Mean change from baseline in GA area at 1 year (48 weeks) in all patients (n=312 per arm)	$\Delta=0.42 \text{ mm}^2$ (approximately 20% ^a reduction) SD= 1.53	88%	0.26 mm^2 (approximately 13% ^a reduction)

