4.5 EFFICACY ANALYSIS

Efficacy analyses will be based on the ITT patient population or microperimetry-analysis population, as appropriate (Section 4.1.1), with patients grouped according to the treatment assigned at randomization. Available data from all randomized and treated patients regardless of adherence to the protocol will be included in the efficacy analyses; this includes data from patients who discontinued study drug early but continued with study assessments.

Unless otherwise noted, hypothesis testing and estimation of treatment effects will be performed with a regression model that includes data from all three treatment arms (sham pooled, lampalizumab Q4W, and lampalizumab Q6W). When analyzing data by biomarker group, separate regression models will be fit for the biomarker-positive and biomarker-negative patient groups (as defined in Section 2.2). All hypothesis tests for efficacy endpoints will be two-sided.

Unless otherwise noted, analyses of efficacy endpoints (primary, secondary, and exploratory) in the overall patient population will be adjusted for the following randomization stratification factors and baseline covariates:

- Biomarker status (positive vs. negative, as determined by the cobas[®] CFI Profile CTA)
- Baseline BCVA ETDRS chart Snellen equivalent (20/50 or better vs. worse than 20/50)
- Sex (male vs. female)
- Baseline GA lesion contiguity (multifocal vs. non-multifocal)

- For efficacy endpoints based on GA area and microperimetry assessments (e.g. number of absolute scotomatous points) only.
- Baseline GA lesion location (subfoveal vs. non-subfoveal)
 - For efficacy endpoints based on GA area, microperimetry assessments (e.g. number of absolute scotomatous points), and visual acuity (BCVA or LLVA) only.

Analyses of efficacy endpoints performed by biomarker group will include the above listed randomization stratification factors and baseline covariates with the exception of biomarker status.

All patients are expected to have the randomization stratification factors and baseline covariates that are specified above. One exception is that a small number of patients do not have a valid baseline BCVA score recorded per the corresponding electronic case report form. In order to include these patients in the efficacy analyses based on regression modeling with covariate adjustment, the BCVA category (20/50 or better vs. worse than 20/50) captured in the IxRS will be used.

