4.5.1.3 Other Subgroup Analyses

Exploratory subgroup analyses will be performed to evaluate the consistency of the primary analysis results across subgroups defined by demographic and baseline characteristics. Analyses will be performed for the primary efficacy endpoint (change from baseline in GA area at Week 48) for each of the following subgroups (as appropriate per actual subgroup sample size):

- Age (<75 years, 75 to <85 years, ≥85 years)
- Sex (male, female)

- Race (White, Black or African American, Asian, American Indian or Alaskan Native, Native Hawaiian or other Pacific Islander, multiple, unknown)
 - Note: If the vast majority of patients (e.g. > 95%) are of a single race, this analysis will not be conducted.
- Geographic region
 - US and Canada
 - Western Europe (Austria, Belgium, Denmark, France, Germany, Italy, Netherlands, Portugal, Spain, Sweden, Switzerland, UK)
 - Rest of World (Argentina, Australia, Hungary, Mexico, Peru, Poland, Russia, Slovakia, Turkey)
- Baseline BCVA (< 64 letters [worse than 20/50], ≥ 64 letters [20/50 or better])
- Baseline low luminance deficit (LLD) (< 30 letters, ≥ 30 letters), where LLD = BCVA - LLVA
 - Note: The median LLD at baseline is expected to be approximately 30 letters based on data from Study GX29633.
- Baseline GA area (≤ 4DA, > 4DA), where 1 disc area (DA) = 2.54 mm²
- Baseline GA contiguity (multifocal, non-multifocal)
- Baseline GA lesion location (subfoveal, non-subfoveal)
- Tobacco use history (ever, never)

Subgroup analyses based on CFI-profile biomarker status are specified in Section [4.5.1.2](#).

For the primary efficacy endpoint, a MMRM similar to that specified for the primary analysis (Section [4.5.1.1](#)) will be used for each subgroup analysis based on the data subset for the patient subgroup of interest. Baseline covariates included in the primary analysis but no longer relevant given the subgroup of interest will be excluded from the model. The estimated treatment effects (lampalizumab vs. sham) and corresponding 95% CIs from the models will be displayed graphically for each lampalizumab treatment arm and each level of the subgroups specified (e.g. via forest plots).

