4.5.2 Secondary Efficacy Endpoints

The secondary efficacy endpoints are listed in Section 2.1.2. At the time of primary analysis, all secondary endpoints will be evaluated based on data from baseline to Week 48 (see Section 2.4). At the time of the final study analysis, all secondary endpoints will be evaluated based on data from baseline to Week 96.

Analysis of secondary efficacy endpoints assessed by mesopic microperimetry will be based on the microperimetry-analysis population. Statistical inferences for efficacy endpoints based on microperimetry assessments will be based on pooled data from Studies GX29176 and GX29185. Analysis of all other secondary efficacy endpoints will be based on the ITT patient population.

Hypothesis testing for three key secondary endpoints will be performed in the order specified in Section 4.5.2.1 based on the Week 96 timepoint. Subgroup analyses (Section 4.5.2.2) for the key secondary efficacy endpoints will be performed.

Treatment-effect related analyses to compare each lampalizumab treatment arm (Q4W or Q6W) and the pooled sham arm for secondary efficacy endpoints will be undertaken as follows. In general, continuous secondary endpoints will be analyzed using a MMRM analysis, with change from baseline as the response variable. For the Week 48 analyses, post-baseline visits, up to and including Week 48, will be included. For the Week 96 analyses, post-baseline visits, up to and including Week 96, will be included. Independent variables for treatment arm, study visit (categorical variable), treatment arm by study visit interaction, baseline value of the endpoint, and the randomization stratification factors and baseline covariates as described in Section 4.5 will be included in the model. An unstructured covariance matrix will be used to model the within-subject errors. If there are convergence problems with the model, then a heterogeneous compound symmetry covariance structure will be used.

In general, binary secondary endpoints will be analyzed using a logistic regression model. The model will include independent variables for treatment arm, baseline value of the endpoint (continuous scale), and the randomization stratification factors and baseline covariates as described in Section 4.5, as appropriate. If the response rate is low, an unadjusted analysis may be performed. Analyses will be based on the observed data for the timepoint, with no imputation for missing data.

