All hypotheses for the key secondary endpoints will be tested for significance at the study level, except for H₀₅. The secondary endpoint of number of absolute scotomatous points will be based on the microperimetry-analysis population, which is estimated to be 10-15% of the total ITT population. Microperimetry was assessed in a subset of patients at selected study sites only. For this secondary endpoint, data from both Studies GX29176 and GX29185 will be combined to achieve a sample size sufficient to evaluate and test for treatment differences with a reliable level of precision.

As a consequence of this, for analyses of secondary efficacy endpoints at the individual study level:

- For H₀₅, the study-level p-value will be presented. However, interpretation of significance in a confirmatory manner will be based on the analysis of pooled data from Studies GX29176 and GX29185.
- H₀₆ will be tested in a confirmatory manner at the study-level if and only if, based on an analysis of pooled data from Studies GX29176 and GX29185, H₀₅ is rejected (i.e., pooled analysis $p \leq 0.0496$).
- H₀₇ will be tested in a confirmatory manner at the study-level if and only if H₀₆ is rejected at the study-level

As noted above, significance testing for H₀₅ will not be done at the study level, but rather interpretation of significance in a confirmatory manner will be based on the analysis of pooled data from Studies GX29176 and GX29185 for the microperimetry-based endpoint.

All hypothesis tests for the secondary endpoints will be on the basis of a two-sided alpha level of 0.0496.

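### The LLVA and monocular reading-speed models leave some collected baseline data unused; adding it could modestly improve precision at almost no cost

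*SAP*

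**What the plan says.** SAP 4.5.2 analyses continuous secondary endpoints by MMRM with treatment arm, visit, their interaction, and "baseline value of the endpoint, and the randomization stratification factors and baseline covariates as described in Section 4.5 will be included in the model". SAP 4.5 lists those factors and covariates: biomarker status, study-eye baseline BCVA in two categories (20/50 or better, or worse), sex, and two lesion descriptors limited to certain endpoints. Lesion location is included as follows: "For efficacy endpoints based on GA area, microperimetry assessments (e.g. number of absolute scotomatous points), and visual acuity (BCVA or LLVA) only".

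SAP 4.5.2 then makes endpoint-specific changes:
- For the BCVA endpoint, continuous baseline BCVA replaces the category. No such change is stated for LLVA.
- For reading speed, chart type (MNRead or Radner) is added.
- For binocular reading speed, baseline BCVA of the better-seeing eye replaces the study-eye category.

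Baseline GA area is a model term in SAP 4.5.1.1, where it is the endpoint's own baseline value. It is not carried into the functional models. SAP 4.4 shows that baseline GA area, lesion location, BCVA and LLVA are all recorded.

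SAP 4.5.1.3 also defines a subgroup variable from two of these baselines, "Baseline low luminance deficit (LLD) (< 30 letters, ≥ 30 letters), where LLD = BCVA - LLVA", and SAP 4.5.2.2 applies the same subgroups to LLVA.

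**The concern.** H06 (LLVA) is a confirmatory test at Week 96, and H07 (binocular reading speed) can be tested only if H06 is rejected. The documents state no power for either. If a baseline variable predicts the outcome beyond the terms already in the model, omitting it leaves the confidence interval wider than necessary. The MMRM also assumes data missing at random given its terms, and further prognostic baselines can make that more plausible.

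There are reasons to expect some prognostic value:
- Protocol 1.1 says that "as the GA lesion expands into the fovea, a profound decrease in central VA occurs", and the SAP already adjusts acuity for lesion location.
- Protocol 3.3.2.1 cites loss of at least three lines at 2 years in about 41% of patients with baseline acuity of 20/50 or better, against 15% of those worse than 20/50 but 20/100 or better.
- Baseline LLVA together with continuous BCVA determines the low luminance deficit exactly. LLVA with a two-level category does not.

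**Working it through.** **Terms in each model (SAP 4.5 and 4.5.2), besides treatment, visit and their interaction**

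| Endpoint | Included | Not included |
|---|---|---|
| LLVA (H06) | baseline LLVA, biomarker status, BCVA category, sex, lesion location | continuous BCVA, GA area |
| Monocular reading speed (study eye) | baseline value, biomarker status, BCVA category, sex, chart type | lesion location, GA area |
| Binocular reading speed (H07) | baseline value, biomarker status, sex, chart type, better-seeing-eye BCVA | study-eye lesion location, GA area |

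**Reproducing the SAP's stated power.** SAP 2.3.2 says that "312 patients per lampalizumab treatment arm and 156 patients per sham arm will provide 88% power" for the primary endpoint, with a difference of 0.42 mm², SD 1.53 mm², 15% dropout and alpha = 0.05 − 4 × 0.0001 = 0.0496. Pooled sham is 2 × 156 = 312.
- Completers per group: 312 × 0.85 = 265.2.
- SE = 1.53 × √(2/265.2) = 0.1329.
- 0.42/0.1329 = 3.161. The two-sided critical value is 1.963.
- Power = Φ(3.161 − 1.963) = 88.5%, or 88.3% with the t distribution. The SAP states 88%.
- Minimum detectable difference: 0.261 mm², against 0.26 stated.

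**Gain from added covariates.** SAP 4.5.2.1 says: "All hypothesis tests for the secondary endpoints will be on the basis of a two-sided alpha level of 0.0496". Let r be the partial R-squared of the added terms beyond those already in the model. The SE is multiplied by √(1 − r), which is worth 1/(1 − r) in sample size, and power becomes Φ[(1.963 + z_power)/√(1 − r) − 1.963]. With an assumed base power of 80%, z_power = 0.842. The values of r are also assumptions.

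| r | SE | Equivalent extra patients | Power |
|---|---|---|---|
| 1% | −0.5% | 1.0% | 80.4% |
| 2% | −1.0% | 2.0% | 80.8% |
| 5% | −2.5% | 5.3% | 82.0% |
| 10% | −5.1% | 11.1% | 84.0% |
| 15% | −7.8% | 17.6% | 86.0% |

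The base power matters little: at r = 5%, 50% becomes 52.0% and 90% becomes 91.4%.

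**Detectable difference at Week 96.** Protocol 6.1 gives 25% dropout by 2 years, for microperimetry only. If it is assumed here too, 312 × 0.75 = 234 per group. The difference detectable with 80% power is then 2.805 × √(2/234) = 0.259 SD at r = 0, 0.253 SD at 5% and 0.246 SD at 10%.

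**Cost.** Three extra parameters against 3 × 234 = 702 patients: 1/(1 − 3/702) = 1.004, or about 0.4% of variance.

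**Two-level versus continuous BCVA.** A simulation with normal data, an assumed BCVA–LLVA correlation of 0.4 to 0.8 and a split at the 40th to 60th percentile found that the category keeps about 37% to 59% of what continuous BCVA adds beyond baseline LLVA.

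**The case against.** The SAP prespecifies a coherent covariate set for each endpoint: the endpoint's own baseline, stratification factors, and lesion terms for named endpoint classes. Nothing in it is contradictory or biased, and a sparse model is a legitimate choice. The documents treat the relation between GA area and function as still open: SAP 4.5.3 will explore it, and SAP Section 1 gives it as one purpose of Study GX29633. The 41% and 15% figures compare the two sides of the 20/50 split that the model already contains, so they do not show how much information lies within each category. All of this stands, and it limits the claim to a possible gain.

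Continuous BCVA also has a cost. SAP 4.5 notes that a small number of patients lack a valid baseline score and keeps them through the IxRS category. A replacement needs its own rule.

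A reader might infer that H07 is under-adjusted in the same way. The documents do not support that. The endpoint is binocular and already adjusts for better-seeing-eye BCVA. When both eyes qualify, the study eye is the one with worse function (Protocol 3.1), so its lesion may matter less for binocular reading. Protocol 1.1 links foveal involvement to central acuity, and lists slower reading among early-stage symptoms.

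These objections do not remove the point for LLVA and monocular reading speed. Both are study-eye measures, the variables are in hand, and the SAP gives no reason for leaving them out.

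**Conclusion.** The omissions are real, and filling them is a low-cost efficiency improvement. If the added terms explain 1% to 5% of the remaining variance, the gain is about 0.4 to 2 power points from an 80% base; at 10% it is about 4 points. Both the partial R-squared and the base power are assumptions, since the documents give no SD, effect size, power or covariate correlation for LLVA or reading speed.

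A reader might go further and infer that the plan demonstrably gives up free precision, or that the low luminance deficit is lost from the LLVA model. Neither follows. The gain is unmeasured, and the LLVA model already holds baseline LLVA, a BCVA category and lesion location, so only what these leave unexplained can be recovered. The validity of H06 and H07 is not affected.

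**What to change.** In SAP 4.5 and 4.5.2, before Sponsor personnel are unmasked for the Week 48 analysis:

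1. In the LLVA model, replace the two-level BCVA category with continuous baseline study-eye BCVA. State a rule that keeps patients without a valid score, for example imputing the mean score of their IxRS category.
2. Add baseline GA area to the LLVA, BCVA, microperimetry and monocular reading-speed models. Because microperimetry inference is pooled with Study GX29185, the term must be specified for the pooled model.
3. Add lesion location (subfoveal or non-subfoveal) to the monocular reading-speed model.
4. Treat study-eye lesion terms for binocular reading speed as optional.

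If the sponsor prefers the present models, a sentence giving the reason would be enough. The cost is SAP wording, the BCVA missing-value rule and two or three degrees of freedom per model. No new data are needed.

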4.5.1 Primary Efficacy Endpoint

The primary efficacy endpoint is the change from baseline in GA area at 1 year (48-weeks) as assessed by FAF. The primary efficacy endpoint will be analyzed for the overall patient population (Section 4.5.1.1), in addition to being analyzed for the

biomarker-positive and biomarker-negative groups separately (Section 4.5.1.2). The hypotheses of interest and Type I error management for analyses of the primary endpoint are specified below, and take precedence over that specified in the study protocol.

The null hypotheses for the primary efficacy endpoint are the following:

- H_{01} : There is no difference between lampalizumab Q4W and sham with regard to mean change from baseline in GA area at Week 48 measured by FAF for the overall patient population.
- H_{02} : There is no difference between lampalizumab Q4W and sham with regard to mean change from baseline in GA area at Week 48 measured by FAF for the CFI-profile biomarker-positive patient population.
- H_{03} : There is no difference between lampalizumab Q6W and sham with regard to mean change from baseline in GA area at Week 48 measured by FAF for the overall patient population.
- H_{04} : There is no difference between lampalizumab Q6W and sham with regard to mean change from baseline in GA area at Week 48 measured by FAF for the CFI profile biomarker-positive patient population.

For hypothesis testing of the primary efficacy endpoint, Type I error will be controlled using a fixed sequencing approach by testing the four hypotheses (H_{01} , H_{02} , H_{03} , and H_{04}) sequentially, beginning with H_{01} . All hypothesis tests for the primary endpoint will be based on a two-sided alpha level of 0.0496. Testing for statistical significance proceeds to a subsequent hypothesis only if the tests for all prior hypotheses are significant at the 0.0496 level. Note, the study will be considered positive if the first hypothesis (H_{01}) is rejected (i.e., if a statistically significant difference is observed when comparing the lampalizumab Q4W arm with the sham pooled arm for the primary efficacy endpoint in the overall patient population).

For the primary efficacy endpoint, a number of additional subgroup analyses (Section 4.5.1.3), sensitivity analyses (Section 4.5.1.4), and supplemental analyses (Section 4.5.1.5) will be performed. Included in the sensitivity analyses are analyses to assess the robustness of the primary analysis results to missing data assumptions.

